## 8. CONSORT CHART

---

## 9. AIMS AND HYPOTHESES

### 10. PRIMARY AIM

The **primary aim** is to determine the effectiveness of HWC in improving blood pressure at 6 months post-randomisation.

The primary hypothesis is that HWC initiated one-month post ( $\pm$  two weeks) of the onset of first-ever in a lifetime minor stroke or onset of TIA will lead to clinically meaningful improvements in lifestyle behaviours resulting in a mean difference of 6 mm Hg change in blood pressure from Baseline to 6 months post-randomisation in the HWC compared to usual care. Recurrent TIA onset is included.

The primary end-point is the difference in the mean change from Baseline in systolic blood pressure at 6 months post-randomisation between UC and HWC. The study is powered to detect a mean difference in change of 6 mm Hg ( $SD \pm 20$  mm Hg) between HWC and UC groups at 6 months post-randomisation.

---

### 11. SECONDARY AIMS

The **secondary aims** are to determine the effectiveness of HWC in improving

1. Overall cardiovascular disease (including stroke) risk at 6 months post-randomisation based on the LS7 compared to Baseline

2. Individual LS7 behavioural risk factors at 3-, 6- 9- and 12- months post-randomisation compared to Baseline
3. Awareness about stroke symptoms, risk factors and their management 6- and 12- months post-randomisation compared to Baseline
4. Quality of life, at 6- and 12- months post-randomisation compared to Baseline
5. Cognitive outcomes at 6-, and 12- months post-randomisation compared to Baseline
6. Mood outcomes compared to Baseline
7. Adherence to CVD medications at 3, 6-, and 9 and 12- months compared to Baseline
8. CVD/adverse outcomes at 12 months post randomisation.
9. Health and service costs at 12 months post randomisation
10. Productivity status at 12 months post randomisation

Secondary outcomes are:

1. systolic blood pressure, total cholesterol, blood glucose at 6-months post randomisation
2. change in proportion of participants in 'high' and 'intermediate' to 'low' risk on LS7 at 6-months post randomisation
3. Stroke risk from Stroke Riskometer – 5- year absolute and relative risk at 6- and 12-months post randomisation
4. Quality of life (EQ5D) at 6-months post randomisation
5. Stroke awareness at 6- and 12-months post randomisation
6. Cognitive assessment score (Montreal Cognitive Assessment)
7. Medication adherence (Self-Efficacy For Appropriate Medication Use Scale (SEAMS))
8. CVD adverse outcomes (fatal and nonfatal stroke, TIA, myocardial infarction and heart failure, death attributable to CVD and all-cause mortality)
9. Healthcare and community service costs assessed as self-reported service use questionnaire at follow up. Productivity status will be self-reported and will include items regarding status (e.g., paid work, voluntary work, homemaker, student, unemployed), hours (e.g., full/part time), compared to hospitalisation pre-stroke status.

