## 18. ASSESSMENTS

There will be a total of five assessments: baseline, 3, 6, 9 and 12 months. Eligible participants will be contacted by CRAs to book appointments for assessments. The baseline and 6-month assessments will be conducted face to face to allow the measurement of the primary outcome metrics for the LS7 (height, weight, blood pressure, blood glucose and blood cholesterol) as well as cognitive assessments. The 3-, 9- and 12-months assessments will be conducted over telephone, at a suitable time.

For face-to-face assessments, the participant will have the option of attending a clinic at one of the three locations at the AUT campuses (AUT North, City or South). Participants travelling to clinics will be provided a petrol or supermarket voucher (NZ \$20) for parking or travel costs.

Participants who are unable to travel to clinic sites will be offered a home visit to conduct the baseline and 6-month assessments.

---

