### 3.5 CASE RECORD FORMS AND QUESTIONNAIRES

#### 20. LIST OF QUESTIONNAIRES

Table 1. List of outcome measures

Outcome measure	Baseline	3	6	12
Demographic Factors: Age, sex, ethnicity, employment, education, marital status	✓			
Event type - stroke and pathological subtypes, or TIA and event date (physician diagnosed)	✓			
Hospitalization details: hospital, date of admission, date of discharge	✓			
Event details (revascularization and planned procedures) from medical records	✓			
Hospital Anxiety and Depression Scale	✓	✓	✓	✓
Stroke awareness (recognition of risk factors, knowledge of actions) [61]	✓	✓	✓	✓
Quality of life (EQ-5D-5L) [62]	✓		✓	
Cognitive functioning by MoCA [63]	✓		✓	
Medication adherence and self-efficacy (SEAMS) REF)	✓	✓	✓	✓
Physical measurements (non-fasting blood test, SBP/DBP, BMI, HR)*	✓		✓	
Absolute and relative 5-year risk of stroke (as measured by Stroke Riskometer app)	✓		✓	
Lifestyle factors (Diet score, physical activity, smoking, alcohol)	✓	✓	✓	✓
CVD outcomes, recurrent events, hospitalisation (stroke, CVD events) self-report and/or from clinical records	✓	✓	✓	✓
Health and Service costs: NMDS (NZ)			✓	✓
Productivity level NMDS (NZ)	✓	✓	✓	✓
Participant feedback questionnaire – Intervention group only	✓	✓	✓	✓

Items will include demographic factors, medical history, lifestyle risk factors, awareness of stroke risk factors, warning signs, symptoms and actions;[64] depression screening test (Hospital Anxiety and Depression Scale) health related quality of life ([EQ-5D-5L](#)),[62] health-care resource

use questionnaire, cognitive assessment (Montreal Cognitive Assessment MoCA) and participant satisfaction questionnaires. See 2 for details of measures collected at each timepoint. Life's Simple 7 score will be calculated from corresponding measurements of smoking, BMI, physical activity, healthy diet score, blood total cholesterol, glucose level and BP.[37]

Table 2. Life's Simple 7

Modifiable factors	Poor health	Intermediate health	Ideal health
Smoking status	Current smoker	Former ≤ 12 months	Never or quit > 12 months
Body mass index	≥ 30 kg/m 	25–29.9 kg/m 	< 25 kg/m 
Physical activity	No physical activity	1–3 times, less than 2.5 hours per week	≥ 4 times per week, 2.5 hours or more
Healthy diet score	0–1 component	2–3 components	4–5 components
Total cholesterol	≥ 240 mg/dL	200–239 mg/dL or treated to goal	< 200 mg/dL

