## 31. SECONDARY END POINTS

Secondary outcomes include: (1) difference in the mean change in the LS7 scale score at 6 months post-randomisation between UC and HWC (2) the change in individual lifestyle components of the LS7 scale (BMI, smoking, physical activity, and diet) at 6 and 12 months; (3) diastolic BP (mmHg); (4) quality of life (EQ-5D-5L), (5) awareness of stroke risk factors and warning signs, (6) medication adherence (7) cognitive outcomes (8) adverse events including hospitalisations; and (9) health service use and costs.

The LS7 scale includes BP, cholesterol, blood glucose, BMI, smoking, physical activity, and diet. The score of LS7 will be calculated by providing 2 points for ideal, 1 point for intermediate, and 0

points for poor status of each of the 7 individual factors. Ideal levels of health factors were: non-smoker or quit >1 year ago; BMI <25 kg/m^2; BP <120/80 mm Hg; total cholesterol <200 mg/dL; fasting blood glucose <100 mg/dL; ≥150 min/week of physical activity; and a healthy diet score (≥4 components). Study participants who were treated to target levels for hypercholesterolemia, hypertension, or diabetes mellitus were classified as intermediate for the respective health factor. Thus, the LS7 summary score will range from 0 to a maximum of 14 points, with a higher score indicating healthier status.

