### 34. INFERENCE ANALYSES

Intention to treat (ITT)[95] analyses and per protocol analysis will be used. To address the primary hypothesis ANCOVA will be used to compare the difference in systolic blood pressure at 6-months post randomisation between the HWC and usual care groups, accounting for baseline stratification factors: (age, gender and ethnicity), referral centres, geographical region and known influential clinical characteristics (e.g., comorbidities). To address the secondary hypotheses linear mixed effects (LME) repeated measures models will be used to investigate the differences in (1) adherence to medication (2) health-related quality of life (3) incidence of new vascular events including death (4) life satisfaction (5) cognition (6) mood) and (7) health service utilisation costs between the HWC and Usual care groups, and by ethnicity (sub-group analysis) at 6-months (plus

life-style and adherence at 1-year post-randomisation. These LMEs will model effect of time (baseline, 3-, 6- 9- and 12-months (medication adherence, lifestyle and awareness at only 12 months), post-randomisation whilst accounting for key demographic stratification factors known to confound with outcomes. Any data not collected within 6-weeks of the follow-up points will be classified as missing data. Baseline covariates of age, sex, most recent blood pressure measure and any additional variables predictive of outcome data will be included in the imputation model.[46] The reasons for missingness and the reasons will be recorded and accounted for. Sensitivity analyses will be conducted to test the assumptions of the model (including a complete case analysis in which only subjects with complete data are included). Familywise error control will be used to account for the multiplicity of tests. Inferences will be based on a 5% significance level and two-sided alternatives.

For the analysis of - CVD adverse outcomes (fatal and nonfatal stroke, TIA, myocardial infarction and heart failure, death attributable to CVD and all-cause mortality), we will use Kaplan-Meier life-test and estimate the hazard ratios (HR) and adjusted HR using time-to-event Cox regression analysis. Time to event analysis will include recurrent events and time-dependant variables where appropriate.

Competing risk method will also be applied to compare the CVD adverse outcomes between the two interventional groups, accounting for mortality outcome.

---

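### Four secondary outcomes have 12-month time points that Table 1 does not schedule and Form F does not restrict, and vascular events and death are assigned a linear mixed model beside the time-to-event analysis

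*Protocol*

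**What the plan says.** Section 11 (Secondary aims) sets 12-month time points for cognition in aim 5, "Cognitive outcomes at 6-, and 12- months post-randomisation compared to Baseline", and for quality of life in aim 4, "Quality of life, at 6- and 12- months post-randomisation compared to Baseline". Secondary outcome 3 in the same section asks for the Stroke Riskometer "5- year absolute and relative risk at 6- and 12-months post randomisation". Outcome 4 gives a different timing for quality of life from aim 4: "Quality of life (EQ5D) at 6-months post randomisation". Section 31 asks for change in the lifestyle components of the LS7, "BMI, smoking, physical activity, and diet) at 6 and 12 months".

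Table 1 (Section 20) has columns for baseline and months 3, 6 and 12. The rows for EQ-5D-5L, MoCA, physical measurements (which include BMI) and the Riskometer are ticked at baseline and 6 months only.

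On visit mode, Section 18 states "The 3-, 9- and 12-months assessments will be conducted over telephone, at a suitable time". Section 29 repeats that month 12 is by telephone only.

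Section 34 assigns linear mixed effects repeated-measures models to seven secondary outcomes. The third is "incidence of new vascular events including death". The same section then plans Kaplan-Meier, Cox and competing-risk analyses for fatal and nonfatal cardiovascular events and all-cause mortality.

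**The concern.** Staff who follow Table 1 will not collect four measures at 12 months that the aims or endpoints ask for. Staff who follow Form F may collect some of them, from some participants and by whatever mode is to hand. Either way, the 12-month comparison in the aims would rest on no data or on data collected inconsistently. A 12-month EQ-5D-5L response that is not asked for at the time cannot be recovered later.

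The modelling issue is separate. Incident events and death are not a repeated continuous measurement, and death ends the series that a repeated-measures model describes. With two methods named for the same kind of events and no statement of which governs, the choice could be made after the data are seen.

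**Working it through.** No figure in the protocol needs reproducing here. The check sets the requested time points beside the schedule, the visit mode and the follow-up form.

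| Measure | Where 12 months is asked for | 12-month tick in Table 1 | In Form F | Does a telephone visit prevent it? |
|---|---|---|---|---|
| MoCA | Section 11, aim 5 | No | Yes, unrestricted | Yes, as planned |
| BMI (measured) | Section 31, item 2 | No | Yes, unrestricted | Yes |
| EQ-5D-5L | Section 11, aim 4 (outcome 4 says 6 months) | No | Yes, unrestricted | No |
| Riskometer | Section 11, outcome 3 | No | Yes, unrestricted | No obstacle shown |

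1. **Schedule.** Four of four measures lack a 12-month tick. A lost column in the text extraction is an unlikely cause, because other rows of the same table (HADS, SEAMS, costs) keep their 12-month ticks.

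2. **Follow-up form.** Appendix C lists Form F for months 3, 6, 9 and 12. It contains the MoCA, EQ-5D-5L, height, weight and BMI, and the Riskometer, none limited to a particular visit. Table 1 and Form F therefore give different instructions.

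3. **Visit mode.** Section 18 explains that baseline and 6 months are face to face so that height, weight, blood pressure, bloods and cognition can be assessed. The MoCA is a paper form (Appendix A) that includes copying a cube and drawing a clock. Measured BMI and this MoCA cannot be obtained by telephone. EQ-5D-5L is a short questionnaire that can be read out. Form F lets the participant complete the Riskometer. Mode is thus an obstacle for two of the four.

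4. **Quality of life.** Aim 4 asks for 6 and 12 months; outcome 4 asks for 6 months. Section 31 and Table 1 name EQ-5D-5L as the quality-of-life measure, so both statements concern the same instrument.

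5. **Nine months.** Aims 2 and 7 use 9 months, and Section 29 defines a 9-month telephone visit. Table 1 has no 9-month column, so nothing in it says what is collected then.

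6. **Event model.** Section 34 gives the mixed model to vascular events and death as item (3) of its list. Its later paragraphs give events of the same kind, with all-cause mortality, to Kaplan-Meier, Cox and competing-risk methods. The time-to-event methods suit the outcome; the linear repeated-measures model does not.

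7. **Costs and utilities.** Aim 9 sets costs at 12 months, and Table 1 ticks costs at 6 and 12 months. The Health Economic Evaluation section derives QALYs from the EQ5D but states no time horizon. Scheduled utilities stop at 6 months.

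**The case against.** The strongest reply is that the data are not shown to be unobtainable. Form F already provides for all four measures at every follow-up and offers clinic, home and video as places of assessment, so an editorial correction to Table 1 might be all that is needed. This stands in part. A reader might infer that 12-month data are absent by design for all 360 participants, or that none of the four endpoints can be estimated. The documents do not support that: they contradict each other, and only measured BMI and the paper MoCA meet a real obstacle. Form F's list of places does not remove it, because Sections 18 and 29 both fix month 12 as a telephone visit.

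A second reply is that Section 34 sets the comparison of its listed outcomes at 6 months, with lifestyle and adherence also at one year. The list of times up to 12 months follows with an unclear parenthesis. So the models do not plainly demand 12-month cognition or quality of life; the aims do. That is correct. It would also be wrong to conclude that ANCOVA must replace the mixed model for outcomes with one follow-up. A mixed model with baseline and one later value is valid, and the choice is a preference.

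A third tempting inference is that half the QALY horizon is unobserved, or that 6-month utility will be carried forward. The protocol states neither a 12-month QALY horizon nor a carry-forward rule.

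Finally, model detail can be left to a statistical analysis plan, which is not at hand. That does not answer the event-model point, because the protocol itself names an unsuitable model for events and death.

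**Conclusion.** The point holds as an internal contradiction over secondary outcomes. Four measures have a requested 12-month time point, no 12-month tick in Table 1 and an unrestricted place in Form F. For two of the four the planned visit mode also rules out the measurement. Aim 4 and outcome 4 disagree on the timing of quality of life, and the 9-month visit is missing from Table 1. Section 34 assigns an unsuitable model to vascular events and death alongside a suitable one.

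The primary endpoint, systolic blood pressure measured face to face at 6 months, is untouched. The conclusion assumes that month 12 remains a telephone visit and that the MoCA is given in the paper version reproduced in the protocol. The remark on utilities matters only if QALYs are set on the same 12-month horizon as the cost aim.

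**What to change.** - **Section 34:** delete item (3) from the mixed-model list, so that the time-to-event methods are the only analysis of vascular events and death. This is a one-line edit.
- **Table 1, EQ-5D-5L:** add a 12-month tick, ask it on the existing call, and bring outcome 4 into line with aim 4. The cost is a few minutes per call. It also gives an observed 12-month utility if QALYs are set on the 12-month cost horizon.
- **Sections 11 and 31, MoCA and measured BMI:** limit both to 6 months, and restrict the matching parts of Form F. The cost is losing the 12-month claim for these two. Keeping it would require a face-to-face visit at month 12.
- **Riskometer:** set one timing and use it in Section 11, Table 1 and Form F.
- **Table 1, 9 months:** add the column and tick what is collected at that call.

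Apart from the extra questionnaire, these are edits to wording, the table and the form.

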## HEALTH ECONOMIC EVALUATION

The net costs and benefits of the intervention compared to the control will be described and reported in accordance with the Consolidated Health Economic Evaluation Reporting Guidelines (CHEERS). [97] For each intervention arm, the probability of resource use and associated costs will be reported. Cost estimates will be presented in terms of direct costs (e.g., healthcare), indirect costs (e.g. lost productivity) and out-of-pocket costs. Unit prices for resources utilised will be sourced from the most appropriate and up-to-date source (e.g., PHARMAC). Costs will be measured in actual prices for the reference year (e.g., 2023). Where prices in 2023 are unavailable, adjustment to the actual price will be made using the published health sector specific deflator/inflators. The overall 'Program Costs' (i.e., non-research related costs associated with providing the intervention) will be deducted from the potential cost-offsets from fewer readmissions or other resource savings. Sensitivity and uncertainty (probabilistic multivariable [Monte-Carlo simulated]) analyses to account for variability in point estimates will be performed to assess the robustness of results.

The analysis will include modelling the potential opportunity cost savings from future strokes averted based on changes in risk profile (e.g., change in absolute 5-year risk of stroke or clinically relevant change in LS7 score). An incremental cost/ quality-adjusted life year (QALY) gained will also be calculated. The EQ5D is the most commonly used in economic evaluations to estimate preference-based outcome measure and will be used to calculate QALYs for the cost utility analysis.[62, 98] Threshold and willingness-to-pay analyses, illustrated using cost effectiveness acceptability curves, will be performed to assess uncertainty in the model parameters or a range of different scenarios, to explore under what conditions HWC could be cost effective and yield potential cost offsets/savings. Potential savings will be calculated using a "case-averted" approach, which estimates the direct and indirect costs savings if the use of HWC leads to annual reduction in stroke incidence. These estimates will be extrapolated to the overall New Zealand population.

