**Section 6: Demographic Information**

6.1. Employment Status prior to stroke/TIA  Full-time: Paid employment for  $\geq 30$  hrs a week  Part-time: Paid employment for 1 to less than 30 hrs a week  Not in Paid Employment OR Paid employment for less than 1 hour per week  Retired

6.2. Current marital status  Married, civil union or de facto relationship  Single  Separated, divorced, or widowed

6.3. Usual dwelling place of participant prior to stroke/TIA  Own home  Rented  Living with friends or family  Retirement village or similar  Boarding house  Other  Unavailable

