17.13 Are you currently in paid employment?

- Yes    No

---

17.13.1. If Yes to 17.13., what number of hours have you usually worked in the past 2 weeks?

---

---

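### Outcome 9 and Table 1 name different sources for costs and productivity, and the case record forms can score change in work status for paid work only

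*Protocol*

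**What the plan says.** Section 11, secondary outcome 9, gives the cost outcome as "Healthcare and community service costs assessed as self-reported service use questionnaire at follow up". On productivity it continues: "Productivity status will be self-reported and will include items regarding status (e.g., paid work, voluntary work, homemaker, student, unemployed", together with hours, set against the status before the stroke.

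Table 1 in section 20 names another source for both. Its rows read "Health and Service costs: NMDS (NZ" and "Productivity level NMDS (NZ", each followed by a closing bracket. The text below the table also lists a health-care resource "use questionnaire, cognitive assessment (Montreal Cognitive Assessment MoCA) and participant satisfaction questionnaires", so section 20 itself mentions two sources without assigning them to cost components.

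The Health Economic Evaluation section treats lost productivity as an indirect cost. It says that programme costs will be "deducted from the potential cost-offsets from fewer readmissions or other resource savings".

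The forms are in Appendix C. Form B item 6.1 records employment before the event as full-time, part-time, retired, or "Not in Paid Employment OR Paid employment for less than 1 hour per week". On Form F, item 17.12 asks whether employment has changed since the event, 17.12.1 lists types of change, 17.12.2 is free text, 17.13 asks "Are you currently in paid employment" and 17.13.1 asks for hours.

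**The concern.** Two passages that define the same outcome name different sources. An analyst who follows section 11 would use the questionnaire for costs and productivity, and one who follows Table 1 would use NMDS for both. Health service use and costs are a listed secondary endpoint (section 31), and section 34 plans a comparison between the arms, so the choice of source affects a reported result.

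The second problem lies in data collection. If a status named in the outcome is not a coded option on the form, no later analysis plan can restore it. A participant who gives up or resumes voluntary work, homemaking or study would show no change in any coded item.

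The third is a missing link. The questionnaire named in outcome 9 does not ask about admissions, yet the economic evaluation expects savings from fewer readmissions.

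**Working it through.** No figure is at stake, so the check sets the passages and form items side by side.

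**1. Source of each component**

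| Component | Section 11, outcome 9 | Section 20, Table 1 |
|---|---|---|
| Service costs | self-reported questionnaire | NMDS |
| Productivity | self-report | NMDS |

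For costs the two could be complementary, since the text under Table 1 also lists a resource use questionnaire. For productivity nothing in section 20 softens the difference: one passage says self-report and the other says NMDS. The protocol does not say what NMDS contains, so nothing is concluded here from its contents.

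**2. The five example statuses of outcome 9 against the forms**

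| Status | Form B 6.1 (before the event) | Form F 17.12 to 17.13.1 (follow-up) | Change scorable? |
|---|---|---|---|
| Paid work | coded, full-time or part-time | coded, yes/no, hours and type of change | yes |
| Unemployed | only within the not-in-paid-work option | only as no paid work, or as having stopped work | approximately |
| Voluntary work | not coded | not coded | no |
| Homemaker | not coded | not coded | no |
| Student | not coded | not coded | no |

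One of the five is coded at both times, one is approximated, and three are coded on neither form. The only place that could hold the missing three is the free text at 17.12.2, which explains an answer about employment change and is uncoded.

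The categories also differ between the forms. Retired is an option at 6.1 and nowhere on Form F. Full-time and part-time are divided at 30 hours a week on Form B, while Form F asks for the hours usually worked over the past two weeks.

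Take a participant without paid work who volunteered before the event and has since stopped. Item 6.1 shows no paid employment, 17.12 shows no employment change, and 17.13 shows no paid employment. The coded record is the same as for someone whose situation never changed.

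**3. Admissions**

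Section 17 of the form covers GP visits, a list of therapy, nursing and other services, home help, other help, employment and privately paid services. It has no admission item.

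Admissions are collected elsewhere. The Serious Adverse Events section classes every hospitalisation, whatever the reason, as an SAE to be reported on Form S. Form S section 3 records the hospital, the admission date, an ICD code for the reason and the discharge date, so length of stay can be derived. What is missing is a sentence that names Form S as the inpatient source for outcome 9. The list of forms in Appendix C describes Form S as a record of events, death and hospitalisation and does not mention costing. The hospitalisation row of Table 1 is qualified by stroke and CVD events, so it does not clearly stand for all-cause admissions.

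**The case against.** The strongest reply has four parts.

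*Two cost sources need not conflict.* Section 20 mentions both, and allocating sources to cost components is often left to an analysis plan or a health economics plan, which is not shown here. This stands in part. It answers the cost row, but not the productivity row, where the labels disagree outright. It also cannot rescue form items that were never collected.

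*The status list is introduced as examples.* This is true, so outcome 9 does not fix five scoring categories. But it does say that status items of that kind will be included and compared with the pre-stroke status, and three of its own examples appear on neither form.

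*Comparison with pre-stroke status is possible.* A reader might infer from the mismatch that no such comparison can be made. The forms do not support that. Item 6.1 gives employment before the event, 17.12 asks about change since the event, and 17.12.1, 17.13 and 17.13.1 add type of change, current paid work and hours. For paid work the comparison can be made.

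*Admissions are recorded.* A reader might infer from outcome 9 and Section 17 that admissions go uncosted. That would require one sentence of section 11 to be the exclusive source and Form S, the SAE rule and the NMDS row of Table 1 to be set aside. The documents do not support it, because the data needed to cost admissions are collected.

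**Conclusion.** The point holds in a limited form. Outcome 9 and Table 1 disagree on the source of productivity and are unreconciled on the source of costs. Change in work status can be scored for paid work only, since three of the five example statuses are coded on neither form and the categories before and after the event do not match. The self-report section omits admissions, and although Form S captures them, no passage links it to outcome 9.

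It does not follow that admissions are left out of the costs or that productivity cannot be compared at all. No monetary size is given, because the documents supply no unit costs or admission rates and show no effect on the difference between the arms.

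Severity is minor: a secondary outcome is affected, and the primary endpoint, sample size and error control are untouched. The form part is the more pressing, because categories not collected cannot be added at analysis. The conclusion assumes that Appendix C shows the form items in full.

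**What to change.** 1. **Work status.** Use one identical status item on Form B (status before the event) and Form F (current status), with the outcome 9 categories plus retired. Alternatively, delete the unpaid statuses from outcome 9 and define productivity by paid work and hours.
2. **Table 1.** Make the productivity row read self-report, in line with section 11.
3. **Outcome 9.** Name the source for each component: admissions from Form S, with NMDS as well if the sponsor intends it, and GP, community and private services from Section 17. If NMDS stays, expand the abbreviation and say which component it serves.

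The cost is wording in section 11 and Table 1 and, under the first option, one item aligned across two forms. The downside is one more question at each follow-up call. Admissions need no new data, because Form S already holds the dates and codes. Deleting the unpaid statuses needs no form change, but then the trial no longer claims to measure those roles.
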